5. CHANGES TO PLANNED ANALYSES

In Section 10.3 of version 4.0 of the protocol, it is specified that a fecal sample will be considered negative for the purposes of SYNBI020 clearance if it is below the quantifiable limit (BQL) or estimated to be below <0.1% of the administered dose. This is clarified in Section 4.8 of the SAP: a sample will only be considered negative for the purposes of SYNBI020 clearance if it is BQL. Additionally, this is described in as note to file.

In Section 10.1 of version 4.0 of the protocol, the populations for analysis are described without detail of the differences in populations for Part 1 and Part 2. This is expanded upon in Section 3.1 of the SAP.

Protocol version 6 amended the number of subjects required for of the interim analysis from what was planned in the original protocol, as described in Section 10.5.

6.2. Data Listings to be Generated

██████	████████████████████	█
██████	████████████████████	█
██████	████████████████████	█
Listing 16.2.3.7	Hepatic Encephalopathy Severity Grading (SAF)	X
Listing 16.2.3.8	Child-Turcotte-Pugh Score and Components (SAF)	X
Listing 16.2.3.9	Model for End Stage Liver Disease and Components (SAF)	X
Listing 16.3.1.1	Venous Ammonia 24-Hour Profile (PD)	X
Listing 16.3.1.2	Daily Fasting Spot Venous Ammonia (PD)	X
Listing 16.3.1.3	Venous Ammonia Area Under the Curve over 24 Hours (PD)	X
Listing 16.4.1.1	Bristol Stool Scale Assessment (MK)	
Listing 16.4.1.2	Fecal Sampling and qPCR Results (MK)	

6.3. Figures to be Generated

Figure Number	Description	At Interim Analysis
Figure 15.1.1.x	Venous Ammonia: Time Profiles by Subject (PD)	X
Figure 15.1.2.1	Venous Ammonia Levels: Time Profiles in Part 2 (PD)	X
Figure 15.1.2.2	Venous Ammonia Levels: Time Profiles in Parts 1 and 2 (PD)	X
Figure 15.1.2.3	Venous Ammonia Levels: Change from Baseline by Time and Treatment in Part 2 (PD)	X
Figure 15.1.2.4	Venous Ammonia Levels: Change from Baseline by Time and Treatment in Parts 1 and 2 (PD)	X
Figure 15.1.2.5	Fasting Venous Ammonia by Patient and Treatment	X
Figure 15.1.2.6	Fasting Venous Ammonia Levels in Part 2	X
Figure 15.1.2.7	Fasting Venous Ammonia Levels in Parts 1 and 2	X
Figure 15.1.3.1	Venous Ammonia Levels: Mean Change from Baseline in AUC ₀₋₂₄ in Part 2 (PD)	X
Figure 15.1.3.2	Venous Ammonia Levels: Mean Change from Baseline in AUC ₀₋₂₄ in Parts 1 and 2 (PD)	X

6.4. Operating Characteristics of the Interim Analysis

An IA will be carried out at N=12 (with the study ongoing), with a possible sample size re-estimation to a maximum of N=40 subjects, or if no sample size re-estimation, a final sample size of N=16.

The study design was simulated 10,000 times under the assumption that the true AUC of average daily ammonia change from baseline to Day 5/6 shows a 20% reduction (-0.22 on the log scale) in the treatment group versus the control group.

Based on previous data, the standard deviation of average daily ammonia was estimated to possibly be as small as 50% of that of spot ammonia (~13 µmol/L on the log scale). For a more conservative estimate, we assumed that the standard deviation could also be as high as that of spot ammonia (~26 µmol/L on the log scale). Additionally, measurements for healthy volunteers in protocol SYNBI020-CP-001 showed that the total standard deviation was 25 µmol/L and the standard deviation between and within subject was ~20 µmol/L and 15 µmol/L, respectively (64% of the total variation). Thus, a more pessimistic standard deviation from this data will be examined as 29 µmol/L (64% of 36 µmol/L), with a less pessimistic standard deviation as 20 µmol/L.

Analysis of Stage 1 ammonia data indicated a within-subject, log-scale residual standard deviation of 0.1324 from a baseline AUC_{0-24/24} of 64.8 µmol/L (approximately 9 µmol/L).

For an IA at N=16, with overall type I error (alpha) set at 0.10 and efficacy p-value set at 0.028, conditional power (CP) will be calculated to drive the decision about whether to increase the sample size. The following boundaries were set: futility boundary at CP=0.30 and efficacy boundary at < 0.028 (one-sided). If the trial is not stopped for efficacy or futility, then if CP≥90%, the trial will continue to completion with a total of 20 subjects, and if CP <90%, the sample size will be increased

to target a CP of 90% up to a maximum sample size 40. The operating characteristics of the design can be seen in the below table:

	Pessimistic SD #1 SD=26 $\mu\text{mol/L}$	Pessimistic SD #2 SD=29 $\mu\text{mol/L}$	Healthy Volunteer SD SD=20 $\mu\text{mol/L}$	Stage 1 Observations SD=9 $\mu\text{mol/L}$ (log-scale SD = 0.1324)
Probability to stop for futility at N=16	41.91%	47.19%	25.07%	0.13%
Probability to stop for efficacy at N=16	36.62%	33.03%	55.32%	99.12%
Probability of increasing beyond 20 $20 < N \leq 40$	21.47%	19.78%	19.61%	0.75%
Overall power	54.73%	48.77%	73.48%	99.87%

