4. STATISTICAL METHODS

4.1. Sample Size Justification

Part 1: The sample size for the sentinel cohort (6 subjects) is primarily designed for empirical evaluation of safety and tolerability in subjects with cirrhosis.

Part 2: A sample of 16 subjects must complete all 3 ammonia AUC intervals (baseline, Day 5, and Day 6) to detect a 20% reduction in average daily ammonia ($AUC_{0-24}/24$, from a baseline of 70 $\mu\text{mol/L}$) with an approximate significance level of 10% and an approximate power of 90%. Significance and power are approximate based on the assumptions below. The number of subjects assumes that the SD of spot ammonia is 9 $\mu\text{mol/L}$, approximately half of the variance is between subject, and that the SD for average daily ammonia is as little as half that of spot ammonia. The spot ammonia SD is based on a weighted average of SD observed in a prior study of ammonia lowering in a similar population. The variability of AUC may be 50% lower than spot ammonia based on the FDA summary basis of approval for glycerol phenylbutyrate for urea cycle disorders.

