4.2. General Statistical Methods and Data Handling

4.2.1. General Methods

All output will be incorporated into Microsoft Excel or Word files, sorted and labeled according to the International Conference on Harmonisation (ICH) recommendations, and formatted to the appropriate page size(s).

Tabulations will be produced for appropriate demographic, baseline, PD, microbiotic-kinetic and safety parameters. For categorical variables, summary tabulations of the number and percentage within each category (with a category for missing data) of the parameter will be presented. For continuous variables, the mean, standard deviation, arithmetic percent coefficient of variation (%CV), geometric mean (geo mean), geometric percent coefficient of variation (geo %CV), median, minimum and maximum values will be presented. For discrete numeric variables (e.g. T_{lag}), the median, minimum, and maximum will be presented.

Formal statistical hypothesis testing will be performed on all primary, secondary [REDACTED] [REDACTED] endpoints with all tests conducted at the 1-sided, 0.10 level of significance. Summary statistics will be presented, as well as confidence intervals on selected parameters, as described in the sections below.

Baseline will be defined as the last scheduled measurement prior to the first IP administration (i.e., pre-dose). If a sequence of baseline measurements is taken pre-dose on the same day, time-matched baseline will be used. If multiple measurements are included within a baseline measurement (e.g., repeated measures at the same nominal time), the arithmetic mean of the multiple samples will be considered the baseline. Unscheduled measurements will only be used as baseline upon consultation with the Sponsor.

For each local laboratory where normal reference range of ammonia has not been locally adequately validated, the normal reference range of ammonia will be defined based on approximately 30 healthy volunteers devoid of any chronic or acute medical conditions and medications with normal liver enzymes. Ammonia sampling, sample processing and analysis will be performed as defined in the SYNBI020-CP-002 protocol and lab manual. The 95th percentile will be used as ULN. Outliers based on visual inspection may be excluded on a case-

by-case basis, and if any outliers are excluded, will be reported in the Changes to Planned Analysis section of the CSR with appropriate notes added to tables and figures where outliers have been excluded.

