4.2.5. Multiple Comparisons/Multiplicity

Multiplicity will be addressed via the Haybittle-Peto stopping boundary method for group sequential designs.

First, the IA will be evaluated against the efficacy p-value of 0.01.

The overall type I error will be fixed at $\alpha = 0.10$, allowing for unequal p-value boundaries at the two looks (IA and final). Further details will be provided in Section 4.6.

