4.3. Interim Analyses

After all N=6 subjects are discharged from the clinic following Part 1, safety data will be examined as an informal review (not a formal IA).

A formal, unblinded IA will be performed on the PD2 population (Part 2 only) after at least 16 subjects have completed dosing in Part 2 and have been discharged from the unit, while enrollment may continue, for a possible final sample size of N=20 (N_{CP}). N_{CP} may be adjusted based on actual enrollment just before the IA decision but will not be less than 20.

It is assumed that baseline average daily ammonia is 70 µmol/L, and the placebo group will show a 0 – 10% reduction from baseline, while the desired reduction for the treatment group is 20% versus placebo. Furthermore, the assumed SD of the difference in the means (desired reduction) is 9 µmol/L. Additional assumptions were examined, and the operating characteristics at the IA for these more pessimistic possibilities are shown in Section 6.4.

If the p-value at the IA is < 0.028 the trial could be stopped for efficacy. Otherwise, conditional power (CP) will be computed at the IA for N=16 subjects. This is the probability that the trial will yield a statistically significant reduction in AUC of average daily ammonia change from baseline greater for the treatment group at the end of the trial if the observed difference at the IA is the TRUE underlying difference and the trial is continued to completion with a total of N_{CP} subjects. If this probability is less than 30%, the Safety Monitoring Committee (SMC) could suggest that the trial be stopped for futility. Otherwise, if the CP is less than 90% the sample size will be boosted to target a conditional power of 90%, up to a maximum of 40 patients. If the CP is greater than 90% and the p-value at the IA is greater than 0.028, the trial will end with N_{CP} subjects.

Conditional power for an active dose versus placebo is derived as follows:

$$C_p(\hat{\Theta}) = 1 - \Phi \left\{ \frac{c_2 - B(t)/t}{\sqrt{1-t}} \right\}$$

Parameter	Description
$\Phi\{x\}$	cumulative distribution function for a $N(0, 1)$ random variable
c_2	Adjusted critical cut-off for the final analysis. Assuming that alpha of 0.028 is spent at the interim analysis for one-sided testing, that the total one-sided alpha

	level is 0.05, and that only one IA occurs at the planned information fraction of 0.80 (=16/20), the adjusted critical cut-off is $c_2 = -1.904$.

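### The operating-characteristics table in SAP 6.4 does not follow from the stated overall alpha of 0.10, and its SD 9 column conflicts with the 90% power claimed in SAP 4.1

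*SAP*

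**What the plan says.** **Design.** SAP 4.3 and 6.4 give sample sizes as totals: an unblinded interim at 16, a planned 20 and a maximum of 40. SAP 2.2 randomizes 1:1, so the interim has 8 per arm. The trial may stop for efficacy at one-sided p < 0.028 and for futility at conditional power below 30%. It finishes at 20 if conditional power is at least 90%, and otherwise the sample size is raised.

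**Alpha.** SAP 4.2.1 has "all tests conducted at the 1-sided, 0.10 level of significance". SAP 4.2.5 has "The overall type I error will be fixed at" 0.10, and 6.4 repeats 0.10 for the simulated design. SAP 4.3 instead derives the final cut-off (1.904 in absolute value) by assuming that the total one-sided "level is 0.05, and that only one IA occurs at the planned information fraction of 0.80".

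**Table (6.4), SD 26 / 29 / 20 / 9 µmol/L.**
- Futility: 41.91 / 47.19 / 25.07 / 0.13%
- Efficacy, "Probability to stop for efficacy at N=16": 36.62 / 33.03 / 55.32 / 99.12%
- Increase: 21.47 / 19.78 / 19.61 / 0.75%
- Overall power: 54.73 / 48.77 / 73.48 / 99.87%

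**Sample size (4.1).** "A sample of 16 subjects must complete all 3 ammonia AUC intervals" to detect a 20% reduction from 70 µmol/L, "with an approximate significance level of 10% and an approximate power of 90" per cent. "The number of subjects assumes that the SD of spot ammonia is 9" µmol/L and that "approximately half of the variance is between subject". SAP 4.3 calls 9 the SD of the difference. SAP 6.4 calls it the within-subject log-scale residual (0.1324) of the daily average.

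**The concern.** SAP 4.3 sends the reader to Section 6 for the behaviour of an unblinded interim that can end Part 2 early or double it. If the table was run under another alpha, or with more information than 8 per arm at the listed SDs supplies, its stopping probabilities and power do not describe the design in the text. Two signs prompted the check. The futility, efficacy and increase rows fill 100% of every column, although 6.4 describes a fourth outcome, finishing at 20. Also, 16 subjects with an SD of 9 have about 90% power at a 10% level in 4.1, yet a 99.12% chance of crossing a stricter level in 6.4. At stake is which alpha and final cut-off govern conditional power and the final test, and what risk of a futility result the sponsor accepts when the drug works.

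**Working it through.** I use 0.028 at the interim, as in 4.3 and 6.4 (4.2.5 also mentions 0.01), and count a reduction as positive.

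**1. Row sums.** 41.91 + 36.62 + 21.47 = 100.00; 47.19 + 33.03 + 19.78 = 100.00; 25.07 + 55.32 + 19.61 = 100.00; 0.13 + 99.12 + 0.75 = 100.00. Nothing is left for finishing at 20.

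**2. Final cut-off.** The interim boundary is Z = 1.911, and the interim and final Z have correlation √0.8. Solving P(Z1 > 1.911 or Z2 > c2) = alpha gives c2 = 1.293 for 0.10 and 1.726 for 0.05. The printed 1.904 gives 0.0398, so it matches neither.

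**3. Decision zones.** By the 4.3 formula, CP = Φ[(Z/√0.8 − c2)/√0.2]. So CP = 30% at Z = √0.8 × (c2 − 0.5244√0.2), and CP = 90% at Z = √0.8 × (c2 + 1.2816√0.2).

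| c2 | Futility below Z | CP 90% at Z | CP at Z = 1.911 | Finish-at-20 zone |
|---|---|---|---|---|
| 1.293 | 0.947 | 1.669 | 97.0% | 1.669 to 1.911 |
| 1.726 | 1.334 | 2.056 | 82.1% | empty |
| 1.904 | 1.493 | 2.216 | 69.9% | empty |

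**4. Cut-off implied by the table.** The printed efficacy row fixes the drift, and the futility row then fixes the cut-off. For a Z test, drift = 1.911 + Φ⁻¹(efficacy) and cut-off = drift + Φ⁻¹(futility). For SD 26: 1.911 − 0.342 = 1.569, then 1.569 − 0.204 = 1.365. For a t test I use the noncentral t on 14 df (critical value 2.084).

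| SD | Implied cut-off, Z | Implied cut-off, t | Futility at alpha 0.10, Z / t | Printed futility | Finish at 20 at alpha 0.10, Z / t |
|---|---|---|---|---|---|
| 26 | 1.365 | 1.493 | 26.7 / 23.1% | 41.91% | 9.4 / 14.9% |
| 29 | 1.401 | 1.529 | 30.0 / 26.3% | 47.19% | 9.2 / 14.5% |
| 20 | 1.372 | 1.517 | 13.6 / 10.8% | 25.07% | 9.3 / 14.7% |
| 9 | 1.274 | 1.496 | 0.04 / 0.02% | 0.13% | 0.4 / 0.6% |

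Allowing for the error of 10,000 runs, the lowest Z values are 1.31, 1.35, 1.32 and 0.97, all above 0.947. Alpha 0.10 is excluded under either test. The cut-offs fit c2 = 1.726 under Z, or c2 = 1.904 under t.

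**5. SD 9 column, 8 per arm.** Noncentrality = δ/(SD × √(2m/8)), with δ/SD = 14/9 (raw) or 0.2231/0.1324 (log). Take m = 1 if 9 is the SD of change. Take m = 1.5 if it is the within-subject SD, since one baseline value and the mean of two days give variance 1 + 1/2.
- m = 1: 3.111 (raw) and 3.370 (log), so the efficacy stop is 83.9% (raw, t) to 92.8% (log, Z).
- m = 1.5: 2.540 and 2.752, so 67.8% to 80.0%.
- Baseline as covariate (4.7.1), m = 0.5 + between-subject share, with share 0.5 (4.1) or 0.64 (6.4): about 79% to 93%.

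The printed 99.12% needs 4.285 (Z) or 4.603 (t). The variance must then be (3.370/4.285)² = 0.62 to (3.111/4.603)² = 0.46 of SD², about half. For a Z test, halving the variance is the same as doubling N.

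The futility stop at alpha 0.10 with these inputs runs from Φ(0.947 − 3.370) = 0.8% (m = 1, log, Z) to 5.6% (m = 1.5, raw, t). The table prints 0.13%.

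**6. SAP 4.1 against 6.4.** A drift of 4.285 gives Φ(4.285 − 1.282) = 99.9% power at one-sided 10%, or Φ(4.285 − 1.645) = 99.6% at two-sided 10%. Conversely, 90% power at 10% gives Φ(1.282 + 1.282 − 1.911) = 74.3% at p < 0.028, or Φ(1.282 + 1.645 − 1.911) = 84.5% if the 10% is two-sided.

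**The case against.** The best defence is that the table follows the working definitions of 4.3 and that only the alpha label in 6.4 is wrong. With 16 subjects a t test is natural, and the t-implied cut-offs (1.493 to 1.529) sit on or near the 1.493 that goes with the printed 1.904. Only the SD 29 column falls outside simulation error, by about 0.014. The finish-at-20 zone is then empty, as the rows show. That part stands: a reader might infer that the table contradicts even the printed cut-off, or that the empty zone is a further error, and neither follows. It does not rescue the stated 0.10, because 1.904 corresponds to about 0.040.

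A second defence keeps 16 / 20 / 40 as totals. If two independent days are averaged with no baseline noise, the variance halves. With a t test, base 70 µmol/L and 1.904, a simulation then comes within about 2 points of the printed rows. This is also fair, but the SAP states no such assumption, and a change from baseline carries baseline noise.

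A reader might instead infer that 16 / 20 / 40 were entered per arm. With alpha 0.05, a Z test and base 64.8 µmol/L, that comes within 3 points. Since half the variance and twice the N look alike, the documents cannot separate these causes, and none should be asserted. For the same reason there is no single figure by which the efficacy stop is overstated.

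The 90% in 4.1 is called approximate, but that cannot stretch to 99.6%. Taking 4.1 literally, with the daily-average SD half of 9, gives a noncentrality of 14/(4.5 × 0.5) = 6.22 and power above 99.9%, so the 90% fails there too.

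**Conclusion.** The point holds on three counts.
- **Alpha.** The table was not produced under overall alpha 0.10. With each printed efficacy figure kept, alpha 0.10 would put futility 11 to 21 points lower in the SD 20 to 29 columns and would send about 9% (Z) or 15% (t) of those runs to a finish at 20.
- **SD 9 column.** The listed N and SD give an efficacy stop of 68% to 93%, depending on what 9 measures, against 99.12% printed.
- **4.1 against 6.4.** The two power claims for 16 subjects cannot both hold on the same inputs. If the inputs differ, one label covers a spot SD, an SD of the difference and a within-subject residual.

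The first count assumes the conditional-power formula and planned fraction of 4.3, and holds for Z and t. The second depends on the variance reading and on the log conversion, which the SAP does not give.

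This should be fixed but does not threaten the trial. Ammonia is a secondary objective and the futility rule is advisory. A reader might infer an inflated type I error, but that error does not depend on this table, and the printed 1.904 is stricter than 0.10 requires.

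**What to change.** - Choose one overall alpha, state its sidedness in 4.2.1, 4.2.5, 4.3 and 6.4, and recompute the matching c2 in 4.3 (1.293 for one-sided 0.10 or 1.726 for 0.05, with 0.028 spent at fraction 0.80).
- Define the SD of 9 once, with its source. State how it enters the variance of the treatment contrast, how SDs in µmol/L are converted to the log scale, and whether the simulated statistic is Z or t.
- Re-run the 6.4 simulation with 16 / 20 / 40 as totals, the stated log-scale model and the chosen alpha. Add a row for finishing at the planned N.
- Restate the 6.4 figures and the power in 4.1 from those inputs.
- Remove the leftover opening sentence of 6.4 that puts the interim at 12 and the final sample at 16.

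The cost is a simulation re-run and SAP text, with no added patients or visits. The stated operating characteristics may become less favourable.
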